10.3.1.2 Potential Cases of Drug-induced Liver Injury

Refer to [Section 10.4 Appendix 4: Liver Safety Monitoring and Assessment] for detailed instructions on drug induced liver injury. Abnormal values in AST and/or ALT concurrent or with abnormal elevations in TBL that meet the criteria outlined in [Section 10.4 Appendix 4: Liver Safety Monitoring and Assessment], in the absence of other causes of liver injury, are considered potential cases of drug-induced liver injury (potential Hy's Law cases) and are always to be considered important medical events and reported per [Section 10.3.6 Reporting Procedures for Serious Adverse Events].

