10.3.6 Reporting Procedures for Serious Adverse Events

The investigator must complete and submit an SAE worksheet containing all information that is required by local and/or regional regulations to the sponsor by fax or email immediately (within 24 hours of awareness).

The investigator must complete and submit the reports as required by local regulation, containing all necessary information, to the competent authority.

The SAE worksheet must be signed by a medically qualified investigator (as identified on delegation of authority log). Signature confirms accuracy and completeness of the SAE data, as well as the investigator causality assessment including the explanation for the causality assessment.

For contact details, see [Contact Details of Sponsor's Key Personnel]. Fax or email the SAE/special situations/product defect worksheet to:

Astellas Pharma Global Development Inc. Global Pharmacovigilance [contact] Email: [contact] (copy [contact])

If there are any questions, or if clarification is needed regarding the SAE, please contact the sponsor's medical monitor/study physician or their designee [Contact Details of Sponsor's Key Personnel].

Follow-up information for the event should be sent promptly (as soon as available but no longer than within 7 days of the initial notification).

Full details of the SAE should be recorded on the medical records, SAE/special situation worksheet and in the eCRF.

The following minimum information is required:

- International study number/study number
- Subject number, sex and age
- Date of report
- Description of the SAE (event and seriousness criteria)
- Causal relationship to the IP (including reason)
- Drug provided (if any)

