10.4 Appendix 4: Liver Safety Monitoring and Assessment

The purpose of this appendix is to provide guidance for the monitoring of drug-induced liver injury during the course of the study. It should be noted that this section does not specify the end-of-study analyses of liver enzymes. The end-of-study liver enzymes analyses will be described in the SAP. Any subject enrolled in a study with active drug therapy and reveals an increase of serum aminotransferases (AT) to $> 3 \times$ ULN or bilirubin $> 2 \times$ ULN should undergo detailed testing for liver enzymes (including at least alkaline phosphatase [ALP], ALT, AST and TBL). Testing should be repeated within 72 hours of notification of the test results. For studies for which a local laboratory is used, alerts will be generated by the local laboratory regarding moderate and severe liver abnormality to inform the investigator and study team. Subjects should be asked if they have any symptoms suggestive of hepatobiliary dysfunction.

Definition of Liver Abnormalities

Confirmed abnormalities will be characterized as moderate and severe where ULN is as shown below.

	ALT or AST		TBL
Moderate	$> 3 \times ULN$	or	$> 2 \times ULN$
Severe	$> 3 \times ULN$	and†	$> 2 \times ULN$

Table 6Moderate and Severe Liver Abnormalities

ALT: alanine aminotransferase; AST: aspartate aminotransferase; TBL: total bilirubin; ULN: upper limit of normal

†Samples taken simultaneously or within maximum 24 hours.

In addition, the subject should be considered to have severe hepatic abnormalities for any of the following:

- ALT or $AST > 8 \times ULN$
- ALT or AST > $5 \times$ ULN for more than 2 weeks
- ALT or AST > 3 × ULN and † TBL > 2 × ULN or INR > 1.5 (if INR testing is applicable/evaluated)
- ALT or AST > $5 \times$ ULN and \dagger (TBL > $2 \times$ ULN in subjects with liver metastases)
- ALT or $AST > 3 \times ULN$ with the appearance of fatigue, nausea, vomiting, right upper quadrant pain or tenderness, fever, rash and/or eosinophilia (> 5%)

[†]Samples taken simultaneously or within a maximum of 24 hours.

The investigator may determine that abnormal liver function results, other than as described above, may qualify as moderate or severe abnormalities and require additional monitoring and follow-up.

Follow-up Procedures

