Confirmed moderate and severe abnormalities in hepatic functions should be thoroughly characterized by obtaining appropriate expert consultations, detailed pertinent history, physical examination and clinical laboratory tests. The study site personnel are to complete the liver abnormality case report form (LA-CRF). Subjects with confirmed abnormal liver function testing should be followed as described below.

Confirmed moderately abnormal liver function tests should be repeated 2 to 3 times weekly, and then weekly or less if abnormalities stabilize or the IP has been discontinued and the subject is asymptomatic.

Severe hepatic liver function abnormalities as defined above, in the absence of another etiology, may be considered an important medical event and may be reported as a SAE. The sponsor should be contacted and informed of all subjects for whom severe hepatic liver function abnormalities possibly attributable to IP are observed.

To further assess abnormal hepatic laboratory findings, the investigator is expected to:

• Obtain a more detailed history of symptoms and prior or concurrent diseases. Symptoms and new-onset diseases are to be recorded as "AEs" within the eCRF. Illnesses and conditions such as hypotensive events and decompensated cardiac disease that may lead to secondary liver abnormalities should be noted. Nonalcoholic steatohepatitis is seen in obese hyperlipoproteinemic and/or diabetic subjects and may be associated with

fluctuating AT levels. The investigator should ensure that the medical history form captures any illness that predates study enrollment that may be relevant in assessing hepatic function.

- Obtain a history of concomitant drug use (including nonprescription medication, complementary and alternative medications), alcohol use, recreational drug use and special diets. Medications are to be entered in the eCRF. Information on alcohol, other substance use and diet should be entered on the LA-CRF or an appropriate document.
- Obtain a history of exposure to environmental chemical agents.
- Based on the subject's history, other testing may be appropriate including:
 - Acute viral hepatitis (A, B, C, D, E or other infectious agents)
 - Ultrasound or other imaging to assess biliary tract disease
 - Other clinical laboratory tests, including INR and direct bilirubin
- Consider gastroenterology or hepatology consultations.

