#### 6.5.2.1 Liver Safety Assessment

The liver safety assessments will be summarized by the categories below based on the measurements from Alkaline Phosphatase (ALP), Alanine Transaminase (ALT), total bilirubin, Aspartate Transaminase (AST) and their combination. These parameters will be based on measurements from the local laboratory.

The subject's highest value during the investigational period will be used.

- ALT >3xULN, >5xULN, >8xULN, >10xULN, >20xULN
- AST >3xULN, >5xULN, >8xULN, >10xULN, >20xULN
- ALT or AST >3xULN, >5xULN, >10xULN, >20xULN
- ALP > 1.5 xULN
- Total Bilirubin >2xULN
- (ALT or AST >3xULN) and (Total Bilirubin >2xULN or INR > 1.5)
- (ALT or AST >3xULN) and ALP <2xULN and Total Bilirubin >2xULN

Note: ALT, AST, ALP and Total Bilirubin results will be classified using the reference ranges supplied by the local laboratories.

The last 2 criteria where 2 or more parameters are evaluated will be with the measurements on the same day or up to 1 day apart (Samples to be taken simultaneously or within a maximum of 24 hours).

The denominator for each criterion will be the number of subjects who have at least one value during the investigational period. The number and percentage of subjects meeting the criteria during the investigational period will be summarized by treatment group.

A scatter plot of Peak AST or ALT data vs. Peak Total Bilirubin data will be presented for mirabegron subjects. Data will be presented as fractions of the ULN (of the local laboratories). In this scatter plot the area for Hy's Law will be presented, where ALT or AST >3xULN and Total bilirubin

>2xULN (ALT, ALT and Total Bilirubin from same blood sample or within a maximum of 24 hours). The area for hyperbilirubinemia (ALT and AST <3xULN and Total bilirubin >2xULN), Temple's corollary (ALT or AST >3xULN and Total bilirubin < 2xULN) will also be presented in this scatter plot.

Laboratory data will be provided in listing format by site and subject for the SAF.

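### Appendix 4 makes SAE reporting of potential Hy's Law cases optional, while Section 10.3.1.2 makes it mandatory under the 24-hour procedure

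*Protocol*

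**What the plan says.** Four pieces of protocol text bear on this.

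- **Section 10.3.1.2** covers ALT and/or AST abnormalities accompanied by raised TBL that meet the Appendix 4 criteria, where no other cause of liver injury is present. It calls these potential Hy's Law cases and says they "are always to be considered important medical events and reported per" Section 10.3.6. It also sends the reader to Appendix 4 for the detailed instructions on drug-induced liver injury.
- **Section 10.3.6** requires the investigator to send the SAE worksheet to the sponsor within 24 hours of awareness.
- **Appendix 4 (Section 10.4), definitions.** The Severe row of the table is ALT or AST > 3 x ULN together with TBL > 2 x ULN. The text below the table adds that "the subject should be considered to have severe hepatic abnormalities for any of the following", and the list that follows repeats the combination: "ALT or AST > 3 × ULN and † TBL > 2 × ULN or INR > 1.5". It also contains categories with no bilirubin component, such as ALT or AST > 8 x ULN.
- **Appendix 4, follow-up procedures.** Of every finding in that severe class for which no other cause is found, the appendix says that it "may be considered an important medical event and may be reported as a SAE". The next sentence reads "The sponsor should be contacted and informed of all subjects for whom severe hepatic liver function abnormalities" and limits this to cases that the study drug might have caused. It gives no deadline.

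**The concern.** Section 10.3.1.2 leaves the investigator no discretion: a potential Hy's Law case is an important medical event and goes through the SAE procedure. Appendix 4 makes both steps, the classification and the report, optional for a class that contains the same cases. A site working from Appendix 4, which is where Section 10.3.1.2 directs it, could reasonably conclude that the 24-hour report is a matter of judgement.

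What is at stake is expedited safety reporting, and possibly whether a rare case is counted as a serious TEAE. The study is meant to support licence renewal and safety surveillance in China, and Appendix 4 itself cites 10% to 50% mortality (or transplant) for Hy's Law injury. Scheduled biochemistry is done only at screening and week 12, so a case would probably surface at the end-of-treatment visit. Only one further contact is scheduled after that, and it may be by telephone.

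**Working it through.** The plan states no figure to reproduce, so the main check is a comparison of texts.

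**Step 1: apply both rules to one subject.** Take ALT or AST > 3 x ULN, TBL > 2 x ULN, and no other explanation.

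| Question | Section 10.3.1.2 | Appendix 4 |
|---|---|---|
| Is the subject covered? | Yes: raised ALT/AST with raised TBL, meeting the Appendix 4 criteria | Yes: Severe row of the table, and the list below it |
| Is absence of another cause required? | Yes | Yes |
| Important medical event? | Always | May be |
| Reported as an SAE? | Yes, per Section 10.3.6 | May be |
| Time limit | 24 hours from awareness | None stated |

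The no-other-cause condition appears on both sides, so it does not separate the two rules.

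**Step 2: look for an exception.** Appendix 4 applies its wording to severe abnormalities as defined above it. It does not carve out the combined criterion or refer back to Section 10.3.1.2.

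**Step 3: set the scope.** Section 10.3.1.2 requires a bilirubin elevation. For ALT or AST > 8 x ULN alone, > 5 x ULN for more than 2 weeks, > 3 x ULN with symptoms, or > 3 x ULN with INR > 1.5 but no qualifying TBL rise, it sets no *always* rule. For those categories *may* contradicts nothing in it.

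**Step 4: check whether another route imposes the same duty.**

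- Liver injury is not among the adverse events of special interest in Section 7.3.6, so 24-hour reporting does not arise that way.
- Section 10.3.2 leaves important medical events to medical or scientific judgement. Section 10.3.1.2 removes that judgement for these cases, and Appendix 4 restores it.
- The sponsor notification in Appendix 4 is a *should* without a deadline and names no SAE worksheet.
- The SAP allows the sponsor to upgrade events (Sections 5.4.1 and 6.5.1). That acts on an event already recorded and sets no 24-hour limit.
- SAP Section 6.5.2.1 tabulates the combined criterion from laboratory values, so the case would appear in the analysis, but only in retrospect.

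**Step 5: how often could it matter?** The documents give no rate for such cases. Assume a per-subject probability p from 1 in 10,000 to 1 in 1,000, and use the planned 249 subjects:

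P(at least one case) = 1 − (1 − p)^249

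- p = 0.0001: 1 − 0.9999^249 = 0.0246; expected cases 249 × 0.0001 = 0.02
- p = 0.001: 1 − 0.999^249 = 0.2205; expected cases 249 × 0.001 = 0.25

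This is the chance that a case occurs, not the chance that one goes unreported.

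**The case against.** The best defence is that the rules are compatible. Appendix 4 speaks generally about a mixed class, Section 10.3.1.2 speaks specifically about one subset, and a specific mandatory rule is normally read as overriding a general permissive one. A site that reports satisfies both. Section 7.3 also places the SAE reporting procedures in Appendix 3, which contains Section 10.3.1.2, whereas Appendix 4 describes itself as monitoring guidance. This lowers the practical risk. It does not settle the matter: a site that does not report has still followed Appendix 4, and the cross-reference for detailed instructions leads there.

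A second point is that the mandatory subset may be narrower than the Severe row. Section 10.3.1.2 refers to potential Hy's Law cases, and the Hy's Law definition in Appendix 4 excludes biliary obstruction and Gilbert's syndrome. That is a fair caution for the redrafting. But a case above both thresholds that meets the narrower definition is still in the Severe class, so the conflict remains on either reading.

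Third, there are safeguards: local laboratory alerts for moderate and severe abnormalities, a dedicated liver abnormality form, mandatory discontinuation in Section 8.1 at the combined threshold, and the sponsor's list of always-serious terms. Together they make a wholly unnoticed case unlikely, and delay is the more realistic failure. None of them sets a 24-hour SAE report.

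Finally, the range of 2.5% to 22% rests on assumed rates. The exclusions for raised liver tests and positive hepatitis serology, and the sparse biochemistry schedule, would lower the number of qualifying or detected cases. The range should be read as an order of magnitude and no more.

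**Conclusion.** The concern holds. For ALT/AST > 3 x ULN with TBL > 2 x ULN and no other cause, the protocol gives a mandatory instruction in one section and a permissive one in another, with nothing to say which prevails. The conclusion rests on the wording alone and not on the assumed event rates. It does not extend to the severe categories without raised bilirubin.

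The consequence is limited to expedited reporting of a rare event and possibly its count as a serious TEAE. Efficacy results are untouched. The change should be made because the text contradicts the protocol's own safety-reporting rule, but the point does not threaten the trial's conclusions.

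Appendix 4 is also softer than the main text on stopping treatment: Section 8.1 requires discontinuation at liver thresholds where Appendix 4 only asks that it be considered. The appendix also mentions liver metastases, which have no place in an overactive bladder trial. Both suggest template text that was not aligned with this protocol.

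**What to change.** Let Section 10.3.1.2 govern. In the follow-up procedures of Appendix 4, state that ALT or AST > 3 x ULN with TBL > 2 x ULN and no other etiology must be reported as an SAE under Section 10.3.6 within 24 hours of awareness, and cross-refer to Section 10.3.1.2. If the sponsor means only cases that meet the Hy's Law definition later in the appendix, the same sentence should say so. Keep the permissive wording for the remaining severe categories, such as > 8 x ULN alone or > 5 x ULN for more than 2 weeks, if that is the intention.

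The cost is one or two sentences of protocol text. Assessments, sample size and analyses do not change.

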10.5 Appendix 5: List of Excluded Concomitant Medications

Any medication used for the management of OAB (including tricyclic antidepressants, 1^{st} generation H1-antagonists and α 1-AR antagonists) and any drugs that are sensitive CYP2D6 substrates with a narrow therapeutic index and sensitive P-gp substrates. Use of these medications is not permitted during the study phase. This list is not exhaustive. In case of doubt, the investigator should contact the local study monitor.

Subjects are allowed to continue ongoing treatment of α 1-AR antagonists, 5 α -reductase inhibitors (5-ARIs) and Phosphodiesterase type 5 inhibitors (PED-Is) in case of use for Benign Prostatic Hyperplasia (BPH).

Anticholinergics/antimuscarinics	Tricyclic/heterocyclic antidepressants	1st generation H1-antagonists†
Darifenacin	Alimemazine/Trimipramine	Tripelennamine
Dicyclomine/Dicycloverine	Amitriptyline	Dimenhydrinate
Fesoterodine	Amoxapine	Clemastine
Flavoxate	Clomipramine	Bromazine
Isopropamide	Desipramine	Orphenadrine
Oxybutynin	Dosulepin/Dothiepin	Doxylamine
Oxyphencyclimine	Doxepine	Carbinoxamine
Propantheline	Imipramine	Diphenhydramine
Propiverine	Lofepramine	Cyclizine
Tolterodine	Maprotiline	Chlorcyclizine
Trospium	Mianserin	Hydroxyzine
Solifenacin	Mirtazapine	Meclizine
	Nortriptyline	
	Protriptyline	
al-AR antagonists	CYP2D6 with narrow therapeutic index	Sensitive P-gp substrates
Tamsulosin	Thioridazine	Digoxin
Alfuzosin	Flecainide	Dabigatran
Doxazosin	Propafenone	
Terazosin	Imipramine	
Silodosin	Desipramine	
Strong CYP3A4 inhibitors	Other	
Itraconazole	Mirabegron (except for study drug)	
Ketoconazole	Botulinum toxin	
Ritonavir	Opioids	
Clarthromycin		

P-gp: P-glycoprotein

†Incidental use for motion sickness is accepted.

10.6 Appendix 6: Clinical Laboratory Assessments

Laboratory tests will be performed according to the Schedule of Assessments [Table 1] and sent to a local laboratory for analysis.

Panel/Assessments	Parameters to be Analyzed
Hematology	Hematocrit
	Hemoglobin
	Mean corpuscular volume
	Mean corpuscular hemoglobin
	Mean corpuscular hemoglobin concentration
	Platelets
	Red blood cell count
	White blood cell count
	White blood cell count differential
Biochemistry	Albumin
	Alanine aminotransferase
	Alkaline phosphatase
	Aspartate aminotransferase
	Bicarbonate
	Blood urea nitrogen
	Calcium
	Chloride
	Corrected serum calcium
	Creatinine
	Creatinine kinase
	Glucose
	Lactate dehydrogenase
	Magnesium
	Phosphate
	Potassium
	Sodium
	Total bilirubin (total and direct)
	Total protein
Uninclusia	
Urinalysis	Leukocyte esterase Nitrites
	pH
	Protein
	Red blood cells
	Human chorionic gonadotropin (female subjects only)
Serology (Plasma/serum)	HAV antibodies (IgM)
	HBsAg
	HBc antibodies
	HCV antibodies
	HIV antibodies
	Syphilis

Table 7Clinical Laboratory Tests

HAV: hepatitis A virus; HBc: hepatitis B core; HBsAg: hepatitis B surface antigen; HCV: hepatitis C virus; HIV: human immunodeficiency virus; IgM: immunoglobulin M

10.7 Appendix 7: Overactive Bladder Symptom Score Questionnaire

OABSS questionnaire (Please circle the score that best applies to your urinary condition during the past week in response to each question).

Question	Score	Frequency

How many times do you typically urinate from waking in the	0	7 or less
morning until sleeping at night	1	8 to 14
	2	15 or more
How many times do you typically wake up to urinate from	0	0
sleeping at night until waking in the morning?	1	1
	2	2
	3	3 or more
How often do you have a sudden desire to urinate, which is	0	Not at all
difficult to control?	1	Less than once a week
	2	Once a week or more
	3	About once a day
	4	2 to 4 times a day
	5	5 times a day or more
How often do you accidentally urinate because you can't	0	Not at all
control the sudden desire to urinate?	1	Less than once a week
	2	Once a week or more
	3	About once a day
	4	2 to 4 times a day
	5	5 times a day or more

10.8 List of Abbreviations and Definition of Key Study Terms

List of Abbreviations

Abbreviations	Description of abbreviations
ACN	Astellas Pharma China, Inc.
AE	adverse event
AESI	adverse events of special interest
ALP	alkaline phosphatase
ALT	alanine aminotransferase
AR	adrenoceptor
AST	aspartate aminotransferase
AT	aminotransferases
BPH	Benign Prostatic Hyperplasia
CIOMS	Council for International Organizations of Medical Sciences
CSR	clinical study report
СҮРЗА	cytochrome P450, family 3, subfamily
CYP2D6	cytochrome P450 2D6
DBP	diastolic blood pressure
DPD	Data Protection Directive
DSMB	Data and Safety Monitoring Board
ECG	electrocardiogram
eCOA	electronic clinical outcome assessment
eCRF	electronic case report form
e-diary	electronic diary
EEA	European Economic Area
ЕоТ	end of treatment

Abbreviations	Description of abbreviations
EPIC	European Prospective Investigation into Cancer and Nutrition
EU	European Union
5-ARIs	5α-reductase inhibitors
FAS	full analysis set
FSH	follicle-stimulating hormone
GCP	Good Clinical Practice
GMP	Good Manufacturing Practices
HAV	hepatitis A virus
HBc	hepatitis B core
HBsAg	hepatitis B surface antigen
HCV	hepatitis C virus
HIV	human immunodeficiency virus
HRQoL	health-related quality of life
HRT	hormone replacement therapy
ICF	informed consent form
ICH	International Council for Harmonisation of Technical Requirements for Pharmaceuticals for Human Use
ICS	International Continence Society
IDL	Imported Drug License
IEC	Independent Ethics Committee
IgM	immunoglobulin M
IND	Investigational New Drug
INR	international normalized ratio
IP	investigational product
IRB	Institutional Review Board
IWRS	Interactive Web Response System
LA-CRF	liver abnormality case report form
LS	least squares
LQTS	long QT syndrome
MMRM	Mixed Models Repeated Measures
MPR	medication possession ratio
NMPA	National Medical Products Administration
NOBLE	National Overactive Bladder Evaluation
OAB	overactive bladder
OABSS	OAB Symptom Score
OCAS	oral controlled absorption system
PED-Is	Phosphodiesterase type 5 inhibitors
P-gp	P-glycoprotein
PPIUS	Patient perception of intensity of urgency scale
PVR	post-void residual
QA	quality assurance
QC	quality control

Abbreviations	Description of abbreviations
QTcF	corrected QT interval by Fredericia
QTLs	quality tolerance limits
RCTs	randomized controlled trials
RSI	reference safety information
(S)AE	serious adverse event or adverse event
SAE	serious adverse event
SAF	safety analysis set
SAP	statistical analysis plan
SBP	systolic blood pressure
SE	standard error
SOP	standard operating procedure
SSRIs	Selective Serotonin Reuptake Inhibitors
SUSAR	suspected unexpected serious adverse reactions
TEAE	treatment-emergent adverse event
TBL	total bilirubin
ULN	upper limit of normal
USM	urgent safety measure
UTI	urinary tract infection
WOCBP	woman of childbearing potential

Definition	of Key	Study	Terms	
------------	--------	-------	-------	--

Terms	Definition of Terms
Baseline	The last non-missing observation prior to first administration of IP, unless otherwise specified.
Endpoint	Variable that pertains to the efficacy or safety evaluations of a study. Note: not all endpoints are themselves assessments since certain endpoints might apply to populations or emerge from analysis of results. That is, endpoints might be facts about assessments (e.g., prolongation of survival).
Enroll	To register or enter a subject into a study. Note: once a subject has received the IP or placebo, the protocol applies to the subject.
Investigational Product	The drug, device, therapy or process under investigation in a study that is believed to have an effect on outcomes of interest in a study (e.g., health-related quality of life, efficacy, safety and pharmacoeconomics).
Investigational period	Period of time where major interests of protocol objectives are observed, and where the test product or comparative drug (sometimes without randomization) is given to a subject and continues until the last assessment after completing administration of the test product or comparative drug.
Post investigational period	Period of time after the last assessment of the protocol. Follow-up observations for sustained adverse events and/or survival are done in this period.
Randomization	The process of assigning subjects to treatment or control groups using an element of chance to determine assignments in order to reduce bias. NOTE: unequal randomization is used to allocate subjects into groups at a differential rate; for example, 3 subjects may be assigned to a treatment group for every 1 assigned to the control group.
Screen failure	Potential subject who signed the ICF, but did not meet one or more criteria required for participation in the study and was not randomized.
Screening	A process of active consideration of potential subjects for randomization in a study.
Screening period	Period of time before entering the investigational period, usually from the time when a subject signs the consent form until just before the test product or comparative drug (sometimes without randomization) is given to a subject.
Study period	Period of time from the first study site initiation date to the last study site completing the study.
Variable	Any quantity that varies; any attribute, phenomenon or event that can have different qualitative or quantitative values.

